5.2 Exclusion criteria

Participants meeting any of the following criteria are not eligible for inclusion in this study.

- 1. Prior exposure to TIM-3 directed therapy at any time.
- 2. History of severe hypersensitivity reactions to any ingredient of study drug(s) (azacitidine, sabatolimab) or monoclonal antibodies (mAbs) and/or their excipients
- 3. Human immunodeficiency virus (HIV) infection not controlled by standard therapy and/or with known history of opportunistic infection. For countries where HIV status is mandatory: HIV status will be tested during screening using a local test.
- 4. Active Hepatitis B (HBV) or Hepatitis C (HCV) infection. Participants whose disease is controlled under antiviral therapy should not be excluded.
- 5. Active acute GvHD grade III-IV according to standard criteria (Appendix 1).
- 6. Active moderate chronic GvHD of the lungs according to NIH consensus criteria (Appendix 2).
 - Active severe chronic GvHD according to NIH consensus criteria.
- 7. Psychiatric disorder that interferes with ability to understand the study and give informed consent or patient information assent for adolescent, and/or impacts study participation or follow-up.

- 8. History of another primary malignancy that is currently clinically significant or currently requires active intervention. Participants who are receiving adjuvant therapy, such as hormone therapy, are eligible.
- 9. Any concurrent severe and/or active uncontrolled infection requiring parenteral antibacterial, antiviral or antifungal therapy (such as severe pneumonia, meningitis, or septicemia)
- 10. Other concurrent severe and/or uncontrolled medical conditions (e.g. uncontrolled diabetes mellitus, chronic obstructive or chronic restrictive pulmonary disease including dyspnoea at rest from any cause) or history of serious organ dysfunction or disease involving the heart, kidney, or liver.
- 11. Other co-morbidity that, in the opinion of the investigator, predisposes the participant to high risk of noncompliance with the protocol.
- 12. Active autoimmune disease requiring systemic therapy (e.g. corticosteroids). Topical, inhaled, nasal and ophthalmic steroids are not prohibited. Replacement corticosteroids therapy is allowed and not considered a form of systemic treatment
- 13. Live vaccine administered within 30 days prior to the first day of study treatment (C1D1)
- 14. Cardiac or cardiac repolarization abnormality, including but not limited to any of the following:
 - a) History of myocardial infarction (MI), angina pectoris, or coronary artery bypass graft (CABG) within 6 months prior to starting study treatment
 - b) Clinically significant cardiac arrhythmias (e.g., ventricular tachycardia), complete left bundle branch block, high-grade AV block (e.g., bifascicular block, Mobitz type II and third-degree AV block)
- 15. Female is pregnant or breastfeeding. Negative serum pregnancy test is required for women of child-bearing potential (WOCBP).
- 16. Women of child-bearing potential, defined as all women physiologically capable of becoming pregnant, unless they are using highly effective methods of contraception during study treatment and for 90 days after the last dose of azacitidine (or as per the respective local label, whichever is longer) and 150 days after the last dose of sabatolimab. Highly effective contraception methods include:
 - Total abstinence (when this is in line with the preferred and usual lifestyle of the subject. Periodic abstinence (e.g., calendar, ovulation, symptothermal, post-ovulation methods) and withdrawal are not acceptable methods of contraception
 - Female sterilization (have had surgical bilateral oophorectomy with or without hysterectomy), total hysterectomy or bilateral tubal ligation at least 6 weeks before taking study treatment. In case of oophorectomy alone, only when the reproductive status of the woman has been confirmed by follow up hormone level assessment
 - Male sterilization (at least 6 months prior to screening/baseline). For female participants on the study the vasectomized male partner should be the sole partner
 - Use of oral (estrogen and progesterone), injected or implanted combined hormonal methods of contraception or placement of an intrauterine device (IUD) or intrauterine system (IUS) or other forms of hormonal contraception that have comparable efficacy (failure rate <1%), for example hormone vaginal ring or transdermal hormone contraception

In case of use of oral contraception women should have been stable on the same pill for a minimum of 3 months before taking study treatment.

Women of non-childbearing potential, defined as women who are physiologically and/or anatomically incapable of becoming pregnant, as now further described:

- They are post-menopausal as evidenced by 12 months of natural (spontaneous) amenorrhea with an appropriate clinical profile (i.e., age-appropriate history of vasomotor symptoms), or,
- they have had bilateral surgical oophorectomy (with or without hysterectomy), total hysterectomy or bilateral tubal ligation at least 6 weeks prior to first dose. In the case of oophorectomy alone, only when the reproductive status of the woman has been confirmed by follow up hormone level assessment, is she considered not of childbearing potential.

If local regulations deviate from the contraception methods listed above to prevent pregnancy, local regulations apply and will be described in the ICF.

- 17. Sexually active males unless they use a condom during intercourse while taking azacitidine and for 3 months after stopping this drug. They should not father a child in this period. A condom is required to be used also by vasectomized men in order to prevent delivery of the drug via seminal fluid. In addition, male participants must not donate sperm for the time period specified above.
- 18. Prior systemic AML/cancer-directed treatments given at any time after aHSCT; or investigational modalities ≤ 5 half-lives or 4 weeks prior to starting study, whichever is shorter. Prior prophylactic use of DLI with or without hypomethylating agent (HMA) is permitted, if DLI is completed ≥ 3 months, and HMA is completed ≥ 4 weeks prior to start of study treatment.
- 19. Participants with BCR-ABL mutant AML who are eligible for post-transplant tyrosine kinase inhibitor therapy as per investigator clinical assessment and local practice guidelines

6 Treatment

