- 3. Treatment of interest: Treatment with sabatolimab or sabatolimab in combination with azacitidine taken for the entire study duration post aHSCT. One estimand for each of the two treatments of interest (sabatolimab in monotherapy and sabatolimab in combination with azacitidine) will be considered.
- 4. Handling of remaining intercurrent events:

- Failure to complete 6 cycles of treatment due to death for any reason or relapse: a participant who dies or has a relapse before completing 6 cycles of treatment will be considered as a non-responder (composite variable strategy).
- Failure to complete 6 cycles of treatment due to reasons other than relapse and death for any reason (including due to adverse events, graft vs host disease for example): all participants with an adequate response assessment (other than "unknown" response) will be taken into account regardless of any study treatment interruption or permanent discontinuation; for a participant who stops the study due to reasons other than relapse or death, we will ask the participant to perform a response assessment 6 months after starting study treatment; a participant with no evidence of hematologic relapse 6 months after starting treatment will be considered as a responder (treatment policy strategy).
- Start of donor leucocytes infusions (DLI) or a new anti-neoplastic therapy before completing 6 cycles of study treatment: a participant who starts a DLI or a new antineoplastic therapy before completing 6 cycles of treatment will be considered as a non-responder (composite variable strategy).
- 5. Summary measure for the primary efficacy estimand is the proportion of participants with no evidence of hematologic relapse with its exact 95% confidence interval for each of the two study treatments of interest: sabatolimab in monotherapy and sabatolimab in combination with azacitidine. The trial will be successful if at least one of the treatments of interest (sabatolimab in monotherapy or sabatolimab in combination with azacitidine) meets both statistical and clinical significance (Section 12.4.2).

The **primary safety estimand for adolescent participants** included in this study is described by the following attributes:

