6.2.2 Prohibited medication

During the course of study treatment, participants must not receive additional investigational drugs or devices, chemotherapy, DLI, other cellular therapies or any other therapies that may be active against cancer or modulate the immune response. Post treatment efficacy follow-up period will end, once a participant develops a hematologic relapse, or start of new therapy for AML.

Additionally, the use of systemic corticosteroids and/or immunosuppressive medications is not allowed while on study treatment unless given for the management of infusion-related reaction, treatment-emergent immune-related adverse events (irAEs), aGvHD and/or cGvHD.

Systemic corticosteroids required for control of infusion-related reactions or irAEs must be tapered and be at non-immunosuppressive doses (≤ 10 mg/day of prednisone or equivalent corticosteroid dose) before the next study administration. If more than 10 mg/day prednisone is used, sabatolimab should be interrupted until the participant receives 10 mg/day or less of prednisone. Topical, inhaled, non-absorbable, nasal and ophthalmic steroids are allowed.

For aGvHD and/or cGvHD, refer to Table 6-4.

The use of systemic steroids and/or other immunosuppressive drugs may be administered for prophylaxis against imaging contrast dye allergy (providing this is ≤ 10 mg/day prednisone or equivalent corticosteroid dose), or replacement-dose steroids in the setting of adrenal insufficiency, or for the management of transient exacerbation of other underlying diseases such as chronic obstructive pulmonary disease requiring treatment for ≤ 3 weeks.

The use of live vaccines is not allowed through the duration of the study treatment and 150 days after the last dose of sabatolimab. Inactivated vaccines, subunit, recombinant, polysaccharide and conjugate vaccines and toxoid vaccines are allowed.

In addition, prohibited medication related to azacitidine will apply according to local/global label.

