9.1 Discontinuation and completion

9.1.1 Study treatment discontinuation and study discontinuation

Discontinuation of study treatment will occur when a participant has documented relapse from CR/CRi or until for any of the reasons described below, and can be initiated by either the participant or the investigator.

The investigator must discontinue study treatment for a given participant if, he/she believes that continuation would negatively impact the participant's well-being.

Study treatment must be discontinued under the following circumstances:

- participant/guardian decision
- Pregnancy

- Use of prohibited treatment as per recommendations in the prohibited treatment (Section 6.2.2)
- Any situation in which study participation might result in a safety risk to the participant
- Any adverse events or laboratory abnormalities that in the judgment of the investigator, taking into consideration the participant's overall status, prevents the participant from continuing the study treatment
- Protocol-defined reasons for treatment discontinuation (see Section 6.1.4 and Section 6.1.5)
- Termination of the study by Novartis

If discontinuation of study treatment occurs due to circumstances other that the protocol defined criteria in Section 6.1.4 and Section 6.1.5, the investigator should make a reasonable effort to understand the primary reason for the participant's premature discontinuation of study treatment and record this information.

Participants who discontinue study treatment or who decide they do not wish to participate in the study further should NOT be considered withdrawn from the study UNLESS they withdraw their consent (see 'Withdrawal of Informed Consent' Section 9.1.2). Where possible, they should return for the assessments indicated in the Assessment Schedule. If they fail to return for these assessments for unknown reasons, every effort (e.g. telephone, e-mail, letter) should be made to contact the participant/pre-designated contact as specified in the lost to follow-up section. This contact should preferably be done according to the study visit schedule.

If the participant cannot or is unwilling to attend any visit(s), the site staff should maintain regular telephone contact with the participant, or with a person pre-designated by the participant. This telephone contact should preferably be done according to the study visit schedule.

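### Exclusion 8 admits participants on adjuvant therapy for another cancer, but Sections 6.2.2 and 9.1.1 prohibit therapy active against cancer and require study treatment to stop, with no adjuvant exception

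*Protocol*

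**What the plan says.** **Eligibility.** Protocol 5.2 opens its list with "Participants meeting any of the following criteria are not eligible for inclusion in this study", so meeting a single criterion is enough to exclude. Criterion 8 concerns another primary malignancy and ends: "Participants who are receiving adjuvant therapy, such as hormone therapy, are eligible". Criterion 18 lists "Prior systemic AML/cancer-directed treatments given at any time after aHSCT". Its only stated exception is "Prior prophylactic use of DLI with or without hypomethylating agent (HMA) is permitted", subject to minimum intervals before study treatment. Adjuvant therapy for another cancer is not mentioned there.

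**Conduct.** Protocol 6.2.2 bars, for the duration of study treatment, "chemotherapy, DLI, other cellular therapies or any other therapies that may be active against cancer or modulate the immune response". Protocol 9.1.1 gives a list of circumstances in which study treatment must stop, and one of them is "Use of prohibited treatment as per recommendations in the prohibited treatment (Section 6.2.2".

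**Referral.** Protocol 6.2.1 tells sites to check each concomitant drug against the exclusion criteria and the prohibited list. It sends doubtful cases, and the question whether an enrolled participant should continue, to the sponsor's medical monitor.

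**Analysis.** Protocol 2.1 says that "a participant who starts a DLI or a new antineoplastic therapy before completing 6 cycles of treatment will be considered as a non-responder". Protocol 12.5.1 censors RFS and GRFS at the start of such therapy and discards MRD samples taken after it. SAP 1.2.1, 2.5.4 and 2.6.1 use the same term. Neither document defines it.

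**The concern.** A participant on continuing adjuvant hormone therapy is exactly the case that exclusion 8 names. A site that follows the eligibility list enrols this person. A site that then follows Sections 6.2.2 and 9.1.1 has to stop study treatment for the therapy that was allowed at entry.

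Three things are at stake:

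- **Consistent conduct.** Sites have no common rule for enrolling such a participant, continuing treatment, or recording a protocol deviation.
- **The safety set.** Section 12.1 requires two full-dose infusions for the dose-determining set unless a DLT has occurred. A stop under 9.1.1 before the second infusion would make a safety run-in participant non-evaluable for a reason unrelated to toxicity.
- **Derivation of the efficacy endpoints.** Admitting people who take anticancer drugs for another disease leaves open whether those drugs can trigger the rules on new anti-neoplastic therapy.

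**Working it through.** The main point is one of textual consistency. It depends on no error rate, power or sample size, so the check follows one participant through the current text: an adult on systemic adjuvant hormone therapy for a previous cancer, started before screening and still continuing.

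1. **Exclusion 8:** eligible, by express wording.
2. **Exclusion 18, timing:** inclusion criterion 4 requires MRD positivity at Day 60 or later after transplant. Someone taking hormone therapy at screening will therefore normally have received it after transplant.
3. **Exclusion 18, scope:** hormone therapy is systemic. If the criterion covers treatment directed at any cancer, the participant is excluded, because the DLI/HMA exception does not apply. If it covers AML only, the participant passes. The text allows both readings. Non-systemic adjuvant therapy would not meet the criterion on either reading.
4. **Section 6.2.2:** the test is whether a therapy may be active against cancer, with no restriction to AML. The section does write out exceptions elsewhere, for example for corticosteroids given for infusion reactions, immune-related events or GvHD, and for replacement-dose steroids. An unwritten exception for adjuvant therapy therefore cannot simply be assumed. Result: prohibited.
5. **Section 9.1.1:** use of a prohibited treatment is on the mandatory list. Result: study treatment must stop.

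Steps 1, 4 and 5 conflict whichever way step 3 is resolved.

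**Effect of the stop on the primary efficacy endpoint.** Under Protocol 2.1, stopping for a reason other than relapse, death, DLI or new anti-neoplastic therapy is handled by treatment policy, with a response assessment 6 months after starting treatment. A stop under 9.1.1 does not by itself make the participant a non-responder.

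**The analysis term.** Continuing the same agent is hard to call new. A switch from one adjuvant agent to another is undecided. Section 6.2.2 ends efficacy follow-up at new therapy for AML, while 2.1, 12.5.1 and the SAP use the term without that limit.

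**Scale of one changed classification, at the planned sizes only:** 1/25 = 4 percentage points in monotherapy and 1/20 = 5 points in the combination. Table 12-2 moves from failure at 7/25 to success at 8/25; Table 12-3 moves from failure at 10/20 to success at 11/20.

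**The case against.** The strongest reply has three parts.

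**The protocol provides a route.** Section 6.2.1 requires a check of each drug and sends doubtful cases to the medical monitor, both before enrolment and for someone already enrolled. This makes it less likely that sites will diverge, so divergence should not be stated as certain. It does not settle the matter, because the monitor is given no rule and Section 9.1.1 is phrased as an obligation.

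**Exclusion 18 need not conflict.** Its reference to transplant and its DLI/HMA exception suit a criterion about the transplanted disease, and a specific permission in exclusion 8 would ordinarily prevail over a general bar. This stands. A reader might infer that the participant is plainly ineligible under exclusion 18; the wording does not support that with confidence. The same argument does not reach Sections 6.2.2 and 9.1.1, which govern conduct rather than entry and refer to cancer in general.

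**The issue is largely past.** SAP 2.1 reports that enrolment was halted in December 2023, so new eligibility wording will change no future enrolment. This also stands. What remains is deviation classification, any continuing treatment decisions, and the definitions used in the final report.

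**Conclusion.** The conflict between exclusion 8 and Sections 6.2.2 and 9.1.1 is real and lies in current text. A participant admitted under the express permission is, as written, due to stop study treatment. The clash with exclusion 18 is conditional on reading it to cover all cancers. The number of participants affected is not given and is probably small.

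Two stronger conclusions are tempting and are not supported:

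- **That a change of hormone agent would be scored as failure, contrary to the clinical question.** The primary efficacy question in Protocol 2.1 itself refers to new antineoplastic therapies without limiting them to AML, so the rule does not depart from it. Nor is it clear that a switch would reach the derivation. The visit schedules have a dedicated antineoplastic-therapy row only after discontinuation, and SAP 2.4.2 summarises such therapy for that period. The supported statement is that the term is undefined for this group.
- **That the fault is worth 4 or 5 percentage points.** Those figures describe one responder in full cohorts of 25 and 20. No affected participant is documented, the cohorts will not be filled, and SAP 2.5.2 says the p-value will not be assessed.

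**What to change.** **Main change.** The sponsor should reconcile exclusions 8 and 18 and Sections 6.2.2 and 9.1.1 so that all four give the same answer for adjuvant therapy of a non-AML malignancy, with any exception present in all of them or in none. Which rule is clinically right is for the sponsor and investigators to decide. Any participant already treated while on such therapy should be classified for protocol deviations under the reconciled rule.

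**Secondary change.** State whether continuing, or switching within, adjuvant therapy permitted under exclusion 8 counts as new anti-neoplastic therapy. Apply that statement in Protocol 2.1 and 12.5.1 and in SAP 1.2.1, 2.5.4 and 2.6.1. Limiting the event to therapy for AML throughout is not a neutral clarification: systemic chemotherapy for another cancer could also suppress AML, and a participant who started it could then count as a responder.

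**Cost.** Wording in three protocol sections for the main change (5.2, 6.2.2 and 9.1.1), and one definition carried into two protocol and three SAP sections for the secondary change. No new participants are needed. The recorded medications may need a medical review to mark therapy given for a non-AML malignancy. The definition should be fixed before database lock. If that point has passed, the final report should state the rule used and list any participant it affects.

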6.1 Study treatment

In this study, the term "investigational drug" refers to the Novartis study drug, sabatolimab (MBG453).

The term "study treatment" refers to the combination of study drugs: sabatolimab plus azacitidine or sabatolimab alone.

All doses prescribed, dispensed to the participant and all dose changes during the study including the reason must be recorded on the appropriate electronic case report form (eCRF) page.

6.1.1 Investigational and control drugs

Table 6-1 Investigational and control drug

Investigatio nal/ Control Drug (Name and Strength)	Dose for Administ ration	Frequency /Regimen	Pharmace utical Dosage Form	Route of Administr ation	Supply Type	Sponsor (global or local)
Sabatolimab	400 mg	Q4W	Solution in	Intravenou	Open label	Sponsor
400 mg/4ml	800 mg		vial for IV infusion	s use		(global)
Azacitidine*	50 mg/m ²	Days 1-5 of each cycle	Vial for IV infusion or	Intravenou s or	Open label	Sponsor (global)
100 mg as per local		Caon Oyolo	subcutane	subcutane		or provided
/global supply			ous administrati on ^{\$}	ous administrati on ^{\$}		locally

^{*} Azacitidine will be used only in the Combination cohort.

Sabatolimab

Sabatolimab will be administered at an assigned dose level, 400 mg or 800 mg, via IV infusion over 30 minutes (up to 2 hours, if clinically indicated) on Day 1 of each 28-day treatment cycle for participants in the sabatolimab monotherapy cohorts; and on Day 5 (+/-3 days except for Cycle 1 where sabatolimab should not be administered earlier than Day 5, after the participant has received at least 5 doses of azacitidine) of each 28-day treatment cycle in the combination cohort. There should be a period of at least 1 hour after the infusion whereby the participant requires close observation.

On days of co-administration of azacitidine and sabatolimab (e.g. on Day 5 of a cycle), the azacitidine should be administered first followed by sabatolimab. A minimum of one hour break between azacitidine administration (IV or SC) must be applied before starting the sabatolimab infusion.

Further instructions for the preparation and dispensation of sabatolimab is described in the Pharmacy Manual.

Azacitidine (Combination Cohort 3 only)

Azacitidine will be administered at a dose of 50 mg/m²; body surface area (BSA) in m² = [height (cm) x weight (kg)/3600]^{0.5}), SC or IV every day for five consecutive days on Days 1-5 out of a 28 days cycle (for further details except the dose and schedule, see local azacitidine prescribing information or (Vidaza (Azacitadine) USPI 2008).

The azacitidine regimen used in this protocol was selected based on the available data from various clinical studies testing azacitidine at different doses and schedules in the post-aHSCT setting as preemptive or maintenance therapy of AML or MDS (de Lima et al 2010, Goodyear et al 2012, Platzbecker et al 2012, Craddock et al 2016, Platzbecker et al 2018). Please refer to Section 1.1, Section 1.2 and Section 4.3 for background, purpose and rationale. Lower doses of azacitidine (50 mg/m² SC x 5 days of every 28-day cycle)

^{\$} Intravenous or subcutaneous azacitidine should not be substituted by oral azacitidine (CC-486, Onureg®). The indications and dosing regimen for intravenous or subcutaneous azacitidine differ from that of oral azacitidine (CC-486, Onureg®).

were selected in attempt to improve tolerability of treatment with likely less hematological toxicities and infectious complications after aHSCT; and to enhance adherence to schedule and protocol compliance by reducing the burden of frequent hospital visits.

Intravenous or subcutaneous azacitidine should not be substituted by oral azacitidine (CC-486, Onureg®). The indications and dosing regimen for intravenous or subcutaneous azacitidine differ from that of oral azacitidine (CC-486, Onureg®).

